4.20.	Patient Instructions	
Instruct the Subject the following:
 
 • The lenses will be worn on a daily wear daily disposable basis. • Enough lenses will be dispensed to the subject to wear for the required number of days until their follow-up visit. Additional “spare” lenses may be dispensed to the subject based on the Investigators discretion. Instruct the subject to bring back all unworn study lenses. • If determined necessary by the Investigator Refresh Plus® sterile non-preserved rewetting drops may be dispensed to be used as needed for dryness. • Subjects will be instructed to wear lenses for a minimum of 6 hours a day every day during the study. • Subjects will be instructed to wear their glasses (if applicable) when not wearing the study lenses. 
Note: In the event a lens is lost or damaged, if no spare lenses are available, the subject will return to the investigator site for replacement. As much as reasonably possible, a damaged lens should be returned to the investigational site and then returned to the Sponsor. If lens damage is present, complete the Product Quality Complaint Form. The lens will be stored in labeled vial with sterile saline and returned to the Sponsor.
	

Visit 4: Treatment 1 Follow-up 2 (2-week follow up)			
Step	Procedure	Details	
4.21.	Wearing Schedule	The test lenses will be worn on a daily wear, daily disposable basis. Note: For this protocol a day of wear is considered to be a minimum of 6 hours. When not wearing the study lenses the participant should be instructed to only wear their glasses (if applicable). For the follow-up visit instruct the participant they must have worn the lenses for at least 2 hours.	
4.22.	Follow-up	The participant will be scheduled to return for their follow-up (V5) appointment in 4 weeks ±6 days from visit #4.	

VISIT 5

The Subjects must present to Visit 5 wearing the study contact lenses for at least 2 hours prior to the visit. If the subject has not worn the lenses for at least 2 hours the subject should be rescheduled.

Visit 5: Treatment 1 Follow-up 3 (6-week follow up)			
Step	Procedure	Details	
5.1.	Adverse Events and Concomitant Medications Review	Record any changes in concomitant medications and any adverse events that may have occurred since the last scheduled study visit.	
5.2.	Subject Reported Ocular Symptoms	If the participant reports ocular symptoms with their lenses, they will be recorded in the Subject Reported Ocular Symptoms eCRF	
5.3.	Wear time and Compliance	Subject's compliance with wearing the study CLs will be recorded. Record the hours/day and day/ week the participant has worn the study lenses and CL wear time on the day of follow-up.	
5.4.	Follow-up PRO (CLUE) Questionnaire	Subjects will complete the PRO (CLUE) Contact Lens performance questionnaires.	
5.5.	Subjective Acceptance	Record whether the subject's distance and near vision with the lenses is acceptable.	

Visit 5: Treatment 1 Follow-up 3 (6-week follow up)

Step	Procedure	Details	
		Note: If the subject's distance and/or near vision is not acceptable with the study lenses the subject will be discontinued. Complete the Final Evaluation.	
5.6.	Entrance LogMAR HCVA Acuity	Record the distance intermediate (1M), and near logMAR visual acuity, to the nearest letter, with the contact lenses (OD, OS, OU).	
5.7.	Lens Fit Assessment	
Evaluate and grade lens centration, primary gaze movement, upgaze movement and tightness (push-up test).
 
The participant should not proceed to wear the lenses if any of the following is observed:
 
 • presence of limbal exposure (appearance of clear cornea) in any gaze • presence of edge lift • presence of unacceptable movement (excessive or insufficient) in all three movement categories (primary gaze, upgaze, and push-up). 
If either lens is deemed unacceptable, the participant will be discontinued from the study. Remove the lenses, perform a slit-lamp evaluation, and complete the Final Evaluation form.
	
5.8.	Lens Removal	Remove and discard the lenses.	
5.9.	Biomicroscopy	Non-dilated Slit Lamp Biomicroscopy will be performed. If the clearance of the fluorescein needs to be expedited, preservative-free rewetting drops or saline may be instilled.	
5.10.	Continuance	Confirm the participant meets the criteria to continue.	
5.11.	Insertion of Study Lenses	
Dispense the participant new lenses that match the original distance and ADD power of the lenses that were removed in Step 5.8 above.
 
Note: If the subject has unworn lenses from Visit 4 allow the subject to use the unworn lenses and dispense enough lenses of the same power to last the subject until their next visit.
	
5.12.	Exit LogMAR HCVA Acuity	Record the distance visual acuity, to the nearest letter, with the contact lenses (OD, OS, OU).	

Visit 5: Treatment 1 Follow-up 3 (6-week follow up)			
Step	Procedure	Details	
		Note that the distance visual acuity must be at least 0.18 logMAR OU. for the lenses to be dispensed and the participant must indicate that their vision is acceptable with the lenses. If the participant does not obtain an acceptable visual response (subjective or objective) remove the lenses, complete the slit-lamp exam and Final Evaluation.	
5.13.	Dispensing Criteria	
For the participant to continue in the study, they must meet all three of the following criteria:
 
 • Distance Binocular Visual acuity is 0.18 or better • The lens fit is acceptable OD and OS • Investigator approval. 
If the Investigator does not approve the dispensing of the study lens, then the study is terminated for that participant.
	
5.14.	Lenses / Solutions	
Subjects will be dispensed enough lenses & solutions to last them until their next visit. Additional “spare” lenses may be dispensed to the subject based on the Investigators discretion. Subjects are permitted to use Refresh Plus® CL rewetting drops with the study lenses. Use of any other artificial tears/lubricating eye drops is not permitted with study CLs.
	
5.15.	Patient Instructions	
Instruct the Subject the following:
 
 • The lenses will be worn on a daily wear daily disposable basis. • Enough lenses will be dispensed to the subject to wear for the required number of days until their follow-up visit. Additional “spare” lenses may be dispensed to the subject based on the Investigators discretion. Instruct the subject to bring back all unworn study lenses. • If determined necessary by the Investigator Refresh Plus® sterile non-preserved rewetting drops may be dispensed to be used as needed for dryness. 	

Visit 5: Treatment 1 Follow-up 3 (6-week follow up)			
Step	Procedure	Details	
		
 Subjects will be instructed to wear lenses for a minimum of 6 hours a day every day during the study. Subjects will be instructed to wear their glasses (if applicable) when not wearing the study lenses. 
Note: In the event a lens is lost or damaged, if no spare lenses are available, the subject will return to the investigator site for replacement. As much as reasonably possible, a damaged lens should be returned to the investigational site and then returned to the Sponsor. If lens damage is present, complete the Product Quality Complaint Form. The lens will be stored in labeled vial with sterile saline and returned to the Sponsor.
	
5.16.	Wearing Schedule	
The test lenses will be worn on a daily wear, daily disposable basis.
 
Note: For this protocol a day of wear is considered to be a minimum of 6 hours. When not wearing the study lenses the participant should be instructed to only wear their glasses (if applicable). For the follow-up visit instruct the participant they must have worn the lenses for at least 2 hours.
	
5.17.	Follow-up	The participant will be scheduled to return for their follow-up (V6) appointment in 6 weeks ±6 days from visit #5.	

VISIT 6

The Subjects must present to Visit 6 wearing the study contact lenses for at least 2 hours prior to the visit. If the subject has not worn the lenses for at least 2 hours the subject should be rescheduled.

Visit 6: Treatment 1 Follow-up 4 (12-week follow up)			
Step	Procedure	Details	
6.1.	Adverse Events and Concomitant Medications Review	Record any changes in concomitant medications and any adverse events that may have occurred since the last scheduled study visit.	

Visit 6: Treatment 1 Follow-up 4 (12-week follow up)			
Step	Procedure	Details	
6.2.	Subject Reported Ocular Symptoms	If the participant reports ocular symptoms with their lenses, they will be recorded in the Subject Reported Ocular Symptoms eCRF	
6.3.	Wear time and Compliance	Subject's compliance with wearing the study CLs will be recorded. Record the hours/day and day/ week the participant has worn the study lenses and CL wear time on the day of follow-up.	
6.4.	Collection of unworn lenses	Collect unworn lenses returned by the participant.	
6.5.	Follow-up PRO (CLUE & MRD) Questionnaires	Subjects will complete PRO (CLUE and MRD) Contact Lens performance questionnaires.	
6.6.	Subjective Acceptance	Record whether the subject's distance and near vision with the lenses is acceptable.	
6.7.	Entrance LogMAR HCVA Acuity	Record the distance, intermediate (1M), and near logMAR visual acuity, to the nearest letter, with the contact lenses (OD, OS, OU).	
6.8.	Lens Fit Assessment	Evaluate and grade lens centration, primary gaze movement, upgaze movement and tightness (push-up test). The participant should not proceed to wear the lenses if any of the following is observed: 
 • presence of limbal exposure (appearance of clear cornea) in any gaze • presence of edge lift • presence of unacceptable movement (excessive or insufficient) in all three movement categories (primary gaze, upgaze, and push-up). 
If either lens is deemed unacceptable, the participant will be discontinued from the study. Remove the lenses, perform a slit-lamp evaluation, and complete the Final Evaluation form.
	
6.9.	Stereo-acuity: near (40 cm) CLs	Record Stereo-acuity using Near Stereo-Acuity test with CLs.	
6.10.	Contrast threshold (CLs)	Record distance contrast threshold with CLs: OD, OS, and OU.	
6.11.	Objective accommodation	Record objective accommodation using WAM 5500 refractometer for 4m, 1m, and 40cm targets	

Visit 6: Treatment 1 Follow-up 4 (12-week follow up)			
Step	Procedure	Details	
	(CLs)	with the CLs. OD, OS. Record the average measurement for each distance OD, OS.	
6.12.	COAS (over the CLs)	Measure the ocular aberrations using COAS 2 secs after blink, OD & OS @ distance target Coma over the Contact lenses.	
6.13.	Lens Removal	Remove and discard the lenses.	
6.14.	Biomicroscopy	Non-dilated Slit Lamp Biomicroscopy will be performed. If the clearance of the fluorescein needs to be expedited, preservative-free rewetting drops or saline may be instilled.	

Final Evaluation

Final Evaluation			
Step	Procedure	Details	
F.1	Post-fit Interview Study CL Performance Occupation Hobbies, Visual Demands, Success Criteria, Reasons for Success/Failure	Questions regarding the study CL performance for the participant's: 
 • occupation and hobbies • Visual demands, eg laptop, shift work, night driving etc. • Success criteria with the study CL • Factors affecting success/failure with the study CL 	
F.2	Investigator Recommendation	Investigator recommendation, if applicable (study CLs suitable/not suitable to prescribe, plus investigator reasons where not suitable is indicated) Proceed with final evaluation	
F.3	Distance Subjective Sphero-cylindrical Refraction	Perform an optimal monocular/binocular distance best sphero-cylindrical refraction and record the visual acuity (OD, OS, OU) to the nearest letter (this is referred to as the best corrected visual acuity, BCVA).	
F.4	Subject Disposition	Indicate the participant completed the study successfully or not. For subjects who discontinue, indicate the reason.	
F.5	PRO (CLUE & MRD) Questionnaires	Subjects will complete the PRO (CLUE and MRD) contact lens performance questionnaires.	

Final Evaluation			
Step	Procedure	Details	
	(Discontinued Subjects Only)		
F.6	Biomicroscopy (Discontinued Subjects if not completed during the visit)	Non-dilated Slit Lamp Biomicroscopy will be performed. If the clearance of the fluorescein needs to be expedited, preservative-free rewetting drops or saline may be instilled.	

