Measurements and Procedures	
Visit 1 (Screening, Baseline):
 
Subjects will attend wearing their habitual contact lenses or if not a contact lens wearer then spectacles (if applicable), they also need to bring any distance / reading spectacles, package of their CLs, lens care solution, and rewetting/lubrication eye drops to the appointment.
 
Consent procedures
 
Demographics, health and medication, habitual correction type, CL wearing history.
 
Subjective responses to CL performance (CLUE questionnaire). If habitual contact lens wearers.
 
CL experience and expectations (Quest-Quant questionnaire)

	
Interview (pre-fit) to identify: Subjects' success criteria; reasons for success/failure; visual demands eg. laptop, shift work, night driving etc.
 
logMAR acuity with habitual contact lenses/spectacles (if applicable): monocular & binocular; distance Auto-refraction & keratometry Refraction including reading addition logMAR acuity (with refraction): monocular & binocular; distance, near (0.4 m), intermediate (1 m) Ocular dominance
 
Unilateral cover test: distance & near (40 cm) Stereo-acuity with refraction: near (40 cm)
 
Fixation Disparity: distance & near (40 cm) Contrast threshold: OD, OS, and OU distance only
 
Non-invasive tear break-up time: OD & OS Objective accommodation with distance refraction (WAM 5500: 4 m, 1 m, and 40 cm target) OD & OS
 
Spherical aberration over bare eye: COAS, 2 secs after blink, OD & OS @ distance target Coma over bare eye Other higher order aberrations over bare eye
 
logMAR acuity with habitual spectacles (if applicable): monocular & binocular; distance
 
Visit 2 (Baseline, Treatment 1):
 
Subjects will attend wearing their habitual spectacles (if applicable)
 
Personality test: BIG5
 
logMAR acuity with refraction: monocular & binocular; distance
 
Blur tolerance with refraction: binocular, 1 m distance only
 
Pupil size: Photopic; OD & OS, distance, intermediate (1 m) & near (40 cm) Pupil size: Scotopic; OD & OS, distance, intermediate (1 m) & near (40 cm)

--	--

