4. STUDY DESIGN AND RATIONALE

4.1. Description of Study Design

This will be a prospective, single group, single-arm, and bilateral dispensing study. There will be no randomization and no masking in this non-controlled single-arm study. There also will be no wash out period. Subjects will be assigned to a single study lens type to be worn bilaterally in daily wear, and daily disposable modality, for at least 6 hours per day every day for approximately 12 weeks.

There will 6 visits in this study:

Visit 1: screening and baseline; eligibility confirmation, Quest questionnaire, pre-fit interview

Visit 2: baseline; personality test, study lens fitting

Visit 3: 1-week; CL power optimization

Visit 4: 2-week assessments with study CLs

Visit 5: 6-week assessments with study CLs

Visit 6: 12-week assessments with study CLs, post-fit interview

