7.2. Detailed Study Procedures

There will be a total of 6 study visits including a screening and baseline visit in this study. The investigator will determine participant eligibility using the inclusion and exclusion criteria. Ineligible Subjects will be discontinued from the study.

All Subjects will attend the study screening visits wearing their habitual spectacles. They will attend the rest of the study visits (3-6) after at least 2 hours of study MF CL wear.

The study procedures per visit are listed in the Table 4 below, with more detailed information provided afterwards. All Subjects will undergo all procedures except for CL insertion/removal training, which is not applicable to habitual CL wearers. One additional separate training session within maximum of 2 weeks from Visit 2 is permitted in the study.

Table 4: Study procedures by visit

Visit Information	Visit 1 Screening Baseline Pre-fit interview	Visit 2 Baseline, personality test, lens fitting & training	Visit 3 1-week Follow-up 1, CL power optimization	Visit 4 2-week Follow- up 2	Visit 5 6-week Follow- up 3	Visit 6 12- week Follow- up 4	Final Evaluation
Time Point	Day 0	Day 0 (1-14 days V1)	Week 1 Day 7± 3 from V2	Week 2 Day 7± 3 from V3	Week 6 Day 28± 6 from V4	Week 1 2 Day 42 ±6 from V5	
Estimated Visit Duration	3.5 hrs	3.5 hrs	2.5 hrs	2.5 hrs	1 hr	2.5 hrs	0.5 hr
Statement of Informed Consent	X						
Demographics	X						
Medical History/Concomita nt Medications	X						
Adverse Event and Concomitant Medications Review	X	X	X	X	X	X	
Habitual visual correction information	X						
Contact Lens wear history	X						
CL experience and expectations (Quest-Quant questionnaire)	X						
Interview (Pre-fit)	X						
Interview (Post-fit)							X
Personality test: BIG5		X					
Entrance distance VA (spectacles) If applicable	X	X					
Entrance VA (CLs)			X	X	X	X	
Blur tolerance with refraction: binocular, 1-meter distance only		X					
Pupil size: Photopic; OD & OS, distance, intermediate (1 m) & near (40 cm) Pupil size: Scotopic; OD &		X					

OS, distance, intermediate (1 m) & near (40 cm), with refraction							
Pupil size Photopic; OD & OS, distance, intermediate (1 m) & near (40 cm) Pupil size: Scotopic; OD & OS, distance, intermediate (1 m) & near (40 cm) with CLs			X				
Auto-refraction & keratometry	X						
Subjective Sphero-Cylindrical Refraction	X						X
Reading addition	X						

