Detailed study procedures at each visit are listed below:

VISIT 1

The Subjects must present to Visit 1 wearing habitual contact lens or if not a contact lens wearer their spectacles (if applicable). If the subject is a habitual contact lens wearer and does not have their contact lenses they must be rescheduled.

Subjects will also will be requested to bring any distance/reading spectacles, package of their CLs, lens care solution, and rewetting/lubrication eye drops to the appointment, if not they must be rescheduled.

Visit 1: Screening			
Step	Procedure	Details	
1.1	Statement of Informed Consent	Each participant must read, understand, and sign the Statement of Informed Consent before being enrolled into the study. The Principal Investigator or his/her designee conducting the informed consent discussion must also sign the consent form. Note: The participant must be provided a signed copy of this document.	
1.2	Demographics	Record the participant’s date of birth, sex, race and ethnicity.	
1.3	Medical History and Concomitant Medications	Questions regarding the Subjects’ medical history and concomitant medications.	
1.4	Presbyopic Symptom Questionnaire	Confirm the subject is either already wearing a presbyopic correction (e.g., reading spectacles over contact lenses, or multifocal spectacles, etc.) or responds positively to at least one symptom on the “Presbyopic Symptoms Questionnaire.	
1.5	Habitual Visual Correction	Questions regarding the participant’s habitual lens/correction type and parameters. All Subjects will be asked about their previous CL wear including history of MF CL wear	
Interview (Pre-fit)			
1.6	CL Wear History, Occupation Hobbies, Visual Demands, Contact lens Success, Reasons for Success / Failure	Questions regarding the participant’s: 
 • Habitual correction • Occupation and hobbies • Visual demands, eg laptop, shift work, night driving, etc. • Success criteria with multifocal contact lenses • Factors affecting success/failure with multifocal contact lenses 	

1.7	Screening Eligibility	
All responses to Screening Inclusion Criteria questions must be answered “yes” and all responses to Exclusion Criteria must be answered “no” for the subject to be considered eligible.
 
If subject is deemed to be ineligible after screening, proceed to Final Evaluation and complete Subject Disposition. Refraction and Biomicroscopy forms are not required.
	
-----	-----------------------	--	--

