Visit 1: Baseline			
Step	Procedure	Details	
1.8	Entrance Distance VA (spectacles) if applicable	
Record distance logMAR high contrast VA with the participant’s spectacles (if applicable): OD, OS, OU.
 
Note: The acuity will be recorded to the nearest letter OD, OS, and OU.
	
1.9	Ocular Symptoms	Subjects will respond to a verbal open-ended symptoms questionnaire.	
1.10	Quest-Quant Questionnaire	The subject will respond to the Quest-Quant Questionnaire.	
1.11	PRO (CLUE) Questionnaire (if applicable)	If Subjects are habitual contact lens wearers they will complete the PRO (CLUE) Contact Lens performance questionnaires.	
1.12	Auto-refraction & Keratometry	Record auto refraction and Keratometry results.	
1.13	Subjective Sphero-Cylindrical Refraction	
Conduct balanced subjective Best Sphero-cylindrical Refraction.
 
Record the refraction and distance logMAR visual acuity to the nearest letter.
 
Note: Best distance monocular visual acuity with sphero-cylindrical refraction must be at least +0.20 logMAR and binocular visual acuity of at least +0.10 logMAR with refraction for the subject to enroll in the study.
	
1.14	Near Add Determination	The near reading addition will be determined using the binocular crossed cylinder technique at 40 cm followed by optimization in a trial frame in step 1.20 below.	
1.15	Ocular Dominance	Determine ocular dominance	

1.16	ADD Refinement	Place the BCC result in the trial frame and refine the near prescription with trial lenses (or flippers) under binocular conditions.	
1.17	Near Visual Acuity	Measure Near logMAR at 40cm with near prescription in a trial frame. Record the near visual acuity OD, OS and OU.	
1.18	Unilateral Cover Test	Record presence/absence of strabismus in each eye (OD, OS) at distance with the Sph-cyl Refraction in Trial Frame. Then record presence/absence of strabismus in each eye (OD, OS) at near (40 cm) with the Sph-cyl Refraction and Near Add in Trial Frame.	
1.19	Biomicroscopy	Non-dilated Slit Lamp Biomicroscopy will be performed. If the clearance of the fluorescein needs to be expedited, preservative-free rewetting drops or saline may be instilled.	

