1.20	Eligibility	All responses to corresponding Screening Inclusion Criteria questions must be answered “yes” and all responses to corresponding Exclusion Criteria must be answered “no” for the participant to be considered eligible. If participant is deemed to be ineligible after baseline, proceed to Final Evaluation and complete Subject Disposition. Biomicroscopy and Sph-cyl Refraction forms are not required.	
1.21	Near Stereo-acuity (40 cm)	Record Stereo-acuity at 40 cm using Near Stereo-Acuity test with the Sph-cyl Refraction and Near Add in Trial Frame.	
1.22	Fixation Disparity	Record distance fixation disparity with the Sph-cyl Refraction in place. Then record near (40 cm) fixation disparity with the Sph-cyl Refraction and Near Add in Trial Frame.	
1.23	Contrast Threshold	Record distance contrast threshold with the Sph-cyl Refraction in a trial frame: OD, OS and OU.	
1.24	Tear Break-Up Time (bare eye)	Measure and record (NITBUT) OD & OS with Placido disc topographer projecting onto tear film.	
1.25	Objective Accommodation	Record objective accommodation using WAM 5500 refractometer for 4m, 1m, and 40cm targets with the distance Sph-cyl Refraction OD & OS in	

		Trial Frame. Record the average measurement for each distance OD, OS.	
1.26	COAS (bare eye)	Measure the ocular aberrations using COAS 2 secs after blink, OD & OS @ distance target Coma over bare OD, OS.	
1.27	Topographer (bare eye)	Baseline imaging for lens centration using Medmont Topographer, over bare eye: OD, OS	
1.28	Exit distance VA	Record distance logMAR HCVA with the participant's spectacles (if applicable): OD, OS, OU.	
1.29	Schedule Follow-up	The subject will be scheduled to return for their next appointment in 1 to 14 days.	

VISIT 2

The Subjects must present to Visit 2 wearing spectacles (if applicable), not having worn any contact lenses (if applicable) on the day of the visit. If the subject is wearing or has worn their lenses the day of the visit they must be rescheduled.

Visit 2: Baseline Treatment 1			
Step	Procedure	Details	
2.1.	Adverse Events and Concomitant Medications Review	Record any changes in concomitant medications and any adverse events that may have occurred since the last scheduled study visit.	
2.2.	Non-Contact Lens Wear Compliance	Confirm the Subject has not worn contact lenses prior to the visit.	

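### The protocol gives two conflicting arrival rules for habitual contact lens wearers at Visit 1; under one of them, the bare-eye baseline measures follow same-day lens wear in wearers but not in neophytes

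*Combined protocol and SAP*

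**What the plan says.** The opening text of Section 7.2 reads "All Subjects will attend the study screening visits wearing their habitual spectacles". It then names Visits 3 to 6 as the remaining visits, so the sentence covers Visits 1 and 2.

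The Visit 1 instructions in the same section read "The Subjects must present to Visit 1 wearing habitual contact lens or if not a contact lens wearer their spectacles (if applicable", and continue: "If the subject is a habitual contact lens wearer and does not have their contact lenses they must be rescheduled". The Synopsis (Measurements and Procedures, Visit 1) agrees with the Visit 1 instructions: "Subjects will attend wearing their habitual contact lenses or if not a contact lens wearer then spectacles (if applicable".

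For Visit 2, Section 7.2 requires spectacles, with subjects "not having worn any contact lenses (if applicable) on the day of the visit". Anyone who has worn lenses that day is rescheduled, and step 2.2 checks this.

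The Visit 1 steps include auto-refraction and keratometry (1.12: "Record auto refraction and Keratometry results"), refraction and ADD (1.13 to 1.16), bare-eye tear break-up time (1.24: "Measure and record (NITBUT) OD & OS with Placido disc topographer projecting onto tear film"), bare-eye COAS aberrations (1.26) and a bare-eye Medmont image (1.27). Section 4.1 adds: "There also will be no wash out period".

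**The concern.** A site cannot follow both arrival rules. The choice matters because the rule given twice, in the Synopsis and the Visit 1 instructions, makes measurement conditions depend on lens-wear history. Habitual wearers would be measured after wearing lenses that day; neophytes would not.

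Section 14.2 mixes previous multifocal wearers, single-vision wearers and neophytes on purpose, without targets. Section 14.6 then relates each secondary endpoint, one at a time, to the success classification. Lens-wear history could plausibly relate to success with a multifocal lens. If it does, a measure that shifts with recent wear can appear related to success when it is not, or a real relation can be blurred. The secondary hypothesis in Section 2.3 names age, sex and ADD power as adjustments. It does not name lens-wear history.

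**Working it through.** The plan gives no figure to reproduce on this point, so the check is a tracing of the schedule followed by an illustration.

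**1. Where the measures are taken (Table 4 and the step lists).**

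| Measure | Visit 1 step | Scheduled again? |
|---|---|---|
| Auto-refraction, keratometry | 1.12 | No |
| Subjective refraction | 1.13 | Final Evaluation (F.3); possible at an unscheduled visit (U.5) |
| Reading ADD | 1.14, 1.16 | No |
| Tear break-up time, bare eye | 1.24 | No; pre-lens version at Visits 3 and 4 |
| Aberrations, bare eye | 1.26 | No; over-lens version at Visits 3, 4 and 6 |
| Medmont image, bare eye | 1.27 | No; over-lens image at Visit 3 |

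None of these is scheduled at Visit 2. For completers, the F.3 refraction comes after about 12 weeks of study-lens wear and at least 2 hours of wear that day, so it does not replace the pre-fit value.

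**2. Lens status at Visit 1.** The visible steps contain no lens removal and no minimum time off lenses. Visits 3 to 6 each have a numbered removal step (3.11, 4.13, 5.8, 6.13).

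**3. What arriving in lenses provides.** Steps 1.8 and 1.28 record acuity in spectacles, and CLUE (1.11) is a questionnaire. Acuity in habitual contact lenses appears only in the Synopsis. No step from 1.8 to 1.28 measures through the habitual lenses.

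**4. Endpoints exposed.** Section 2.2 lists 15 secondary endpoints. At most six draw on these measures: auto-refraction/keratometry, refraction with ADD, tear break-up time, spherical aberration, coma and other higher-order aberrations. The last four also have over-lens values, and Section 14.6 does not say which visit enters the model.

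**5. Illustration of size (all inputs assumed).** Let half of 50 subjects be habitual wearers. Let same-day wear shift a measure by d SD, and let the measure have no true relation to success. The expected spurious difference between success groups is

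d × (share of wearers among successes − share of wearers among non-successes).

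- Success 70% in both wear groups: 0.35/0.70 − 0.15/0.30 = 0.50 − 0.50 = 0.
- Success 80% in wearers, 60% in others: 0.40/0.70 − 0.10/0.30 = 0.571 − 0.333 = 0.238. At d = 0.5 this is 0.12 SD; at d = 0.8, 0.19 SD.
- Success 80% and 40%: 0.40/0.60 − 0.10/0.40 = 0.667 − 0.250 = 0.417. At d = 0.5 this is 0.21 SD; at d = 0.8, 0.33 SD.

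Simulated false-positive rates (logistic likelihood-ratio test at 5%, no covariates, 1,500 runs per setting):

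| Success, wearers / others | d = 0 | 0.3 | 0.5 | 0.8 |
|---|---|---|---|---|
| 70% / 70% | 6.8% | 4.9% | 6.0% | 5.9% |
| 80% / 60% | 5.7% | 6.9% | 8.5% | 9.7% |
| 80% / 40% | 6.3% | 9.3% | 10.7% | 19.9% |

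The Monte Carlo standard error is about √(0.06 × 0.94 / 1500) = 0.6 percentage points, and the no-shift rates already sit near 6%. With lens-wear status in the model, the rates lie between 5.1% and 7.8% in all settings.

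A separate t-test simulation (20,000 runs, success 85% and 60%) gives 7.3% and 11.2% at shifts of 0.5 and 0.8 SD with half the subjects wearers, and 6.8% and 8.8% with one third. It gives 4.6% to 5.3% when success is 70% in both groups.

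**The case against.** The strongest reply is that this is a wording slip with little consequence. Its parts differ in weight.

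- **Redaction.** The appendices on refraction, near ADD, keratometry, COAS and Medmont are blacked out and may specify time off lenses. This stands: the gap can be asserted only for the visible text.
- **Order of steps.** Spectacle acuity at step 1.8 implies that lenses are off by then, and tear break-up time, COAS and topography come late in a 3.5-hour visit. This stands in part. Some time off lenses is likely, but step 1.8 is conditional, the interval is uncontrolled, and auto-refraction follows soon after at step 1.12.
- **Wash-out.** A reader might infer that Section 4.1 rules out any lens-free interval. It does not: Visit 2 requires a lens-free day under the same design statement.
- **Lens power.** A reader might infer that a disturbed refraction carries through to the fitted lens. Over-refraction and up to two modifications at Visit 2, and again at Visit 3, largely deal with that.
- **Covariates.** Section 14.5 offers age, sex and ADD power as examples, so lens-wear status could be added. True, but neither Section 14.5 nor Section 2.3 names it.
- **Exploratory purpose.** Section 14.2 disclaims a power basis. That limits the harm of a false lead; it does not justify collecting baseline data under two conditions.
- **Incomplete remedy.** A lens-free day does not undo wear on earlier days. This stands and is carried into the fix.

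**Conclusion.** The contradiction is certain. If sites follow the Synopsis and Visit 1 instructions, the difference in same-day wear follows directly. If they follow the opening text of Section 7.2, it shrinks but may not vanish, because that sentence does not forbid lens wear earlier in the day.

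Confounding of the secondary models is possible, not shown. It requires that Visit 1 values enter those models, that same-day wear moves the measure, and that success differs by wear group. The rates above depend on assumed shifts, success rates and wearer shares, and on tests simpler than the planned model. They show direction and rough scale only. Reading them as this trial's error rate would go beyond the documents.

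Nor do the documents support calling Visit 1 the only source of refraction or corneal findings. Subjective refraction recurs at Final Evaluation, and slit-lamp examination is scheduled at every visit, including Visit 2. The limitation applies to the pre-fit refraction and ADD, auto-refraction, keratometry and the bare-eye instrument measures. It should be corrected because most of these values are never retaken and the correction is cheap.

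**What to change.** Reconcile the Synopsis, the opening text of Section 7.2 and the Visit 1 instructions, so that the bare-eye Visit 1 measures are taken under one lens-wear condition for all subjects. The simplest way is to apply the Visit 2 rule at Visit 1: spectacles if applicable, no contact lens wear that day, rescheduling if lenses were worn, and a check like step 2.2. Wearers bring their lenses and packaging and complete CLUE about their habitual lenses. If the Synopsis acuity in habitual lenses is kept, take it after step 1.27. If a redacted appendix already sets a time off lenses, cite it in the steps.

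In Section 14.6, name the visit whose value enters each model, and add a sensitivity analysis by habitual lens-wear category.

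Cost: amendment text and a changed appointment instruction. Habitual wearers go without lenses for part of one more day, and lenses must be inserted at the end of the visit if the habitual-lens acuity is kept. No data from steps 1.8 to 1.28 are lost. Wear on earlier days remains, which is why the sensitivity analysis is worth adding.
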